6.1.1. Tender/Swollen Joint Counts (TJC/SJC)

Tender joint count based on 68 joints (TJC68) and swollen joint count based on 66 joints (SJC66) will be collected during the course of the study. The assessment for each joint will be from the following selections: Tender Only, Swollen Only, Tender and Swollen, Joint Non-Evaluable or Missing, or Not Tender or Swollen.

Individual joint with missing assessment will not be imputed. If at least half of the joints are assessed at a given visit, the prorated tender and swollen joint counts will be calculated using the following formula:

$$TJC68 = \frac{\text{Total number of tender joints}}{68 - (\text{Number of nonevaluable or missing joints out of 68 joints})} \times 68$$

$$SJC66 = \frac{\text{Total number of swollen joints}}{66 - (\text{Number of nonevaluable or missing joints out of 66 joints})} \times 66$$

If less than half of joints are assessed at a given visit, joint counts are treated as missing for that visit.

A more abbreviated assessment considering 28 joints as listed in Table 6-1 for both tenderness and swelling will also be conducted (as part of the TJC68 and SJC66 assessment), denoted as TJC28 and SJC28, respectively.

Table 6-1. Composition of the 28 Joints

Joints	Number
Shoulder Joints (Left and Right)	2
Elbow Joints (Left and Right)	2
Wrist Joints (Left and Right)	2
Metacarpophalangeal Joints I-V (Left and Right) – hands only	10
Proximal Interphalangeal Joints I-V (Left and Right) – hands only	10
Knee Joints (Left and Right)	2

If there exist non-evaluable or missing joints among the 28 joints, similar prorated tender and swollen joint counts will be calculated as follows:

$$TJC28 = \frac{\text{Total number of tender joints}}{28 - (\text{Number of nonevaluable or missing joints out of 28 joints})} \times 28$$

$$SJC28 = \frac{\text{Total number of swollen joints}}{28 - (\text{Number of nonevaluable or missing joints out of 28 joints})} \times 28$$

If less than half of the 28 joints are assessed at a given visit, TJC28 and SJC28 are treated as missing for that visit.

6.1.2. Global Assessment of Disease Activity

Subject’s Global Assessment of Disease Activity (SGA) and Physician’s Global Assessment of Disease Activity (PGA) based on a 0-100 mm visual analog scale (VAS) will be recorded during the study, with 0 indicating “no disease activity” and 100 indicating “maximum disease activity” (or similar description of disease severity).

6.1.3. Health Assessment Questionnaire Disability Index (HAQ-DI)

The HAQ-DI score is defined as the average of the scores of eight functional categories (dressing and grooming, arising, eating, walking, hygiene, reach, grip, and other activities), administered by the subject. Responses in each functional category are collected as: without any difficulty; with some difficulty; with much difficulty; unable to do a task in that area and with or without aids or devices. The HAQ-DI score ranges from 0 (no disability) to 3 (completely disabled), when 6 or more categories are non-missing. Detailed algorithm for calculating HAQ-DI score is described in [Appendix 2](#).

HAQ-DI also includes a separate pain assessment and subject will be requested to mark the severity of the pain in the past week on a 0-100 mm VAS, with 0 indicating “no pain” and 100 indicating “severe pain”.

6.2. Primary Efficacy Endpoint

The primary efficacy endpoint is the proportion of subjects who achieve ACR20 response at Week 12.

6.2.1. Definition of the Primary Efficacy Endpoint

A subject achieves ACR20 response when this subject has

- $\geq 20\%$ improvement from baseline in TJC68, AND
- $\geq 20\%$ improvement from baseline in SJC66, AND
- $\geq 20\%$ improvement from baseline in at least 3 of the following 5 items:
 - 1) PGA
 - 2) SGA
 - 3) Subject’s pain assessment
 - 4) HAQ-DI score
 - 5) hsCRP

Percent improvement from baseline at a postbaseline visit is calculated as follows for all 7 components mentioned above:

$$\% \text{ improvement} = \frac{\text{baseline value} - \text{postbaseline value}}{\text{baseline value}} \times 100$$

If the baseline value is 0 then the percent improvement from baseline is set to missing.

In the case that some ACR20 components are missing, the ACR20 assessment will be based on the non-missing components. If non-missing components are not sufficient to determine ACR20 response, then the ACR20 response will be considered as missing.

6.2.2. Statistical Hypothesis for the Primary Efficacy Endpoint

In the primary analysis, the ACR20 response rate at Week 12 in the filgotinib 200 mg group will be compared to placebo group for a superiority test at the 2-sided 0.05-level. If we denote the ACR20 response rate at Week 12 in the filgotinib 200 mg group and placebo group as P_1 and P_2 , respectively, the null and alternative hypotheses for the superiority test on the primary efficacy endpoint are as follows:

$$H_0: P_1 = P_2$$

vs

$$H_1: P_1 \neq P_2$$

6.2.3. Primary Analysis of the Primary Efficacy Endpoint

To test for superiority of filgotinib 200 mg group versus placebo control group in proportion of subjects who achieve ACR20 at Week 12, a logistic regression analysis with treatment groups and stratification factors in the model will be used. The model will include all treatment groups. Subjects who do not have sufficient measurements to establish efficacy at Week 12 will be considered as failures (ie, NRI). The p-value from the logistic regression model for testing the superiority of filgotinib 200 mg as compared to placebo will be provided. The 2-sided 95% confidence interval (CI) of the ACR20 response rate at Week 12 based on normal approximation with the sample variance will be provided for each treatment group. In addition, non-stratified ACR20 response rate difference along with its 95% CI calculated based on the normal approximation with the pooled sample variance will be provided. [Appendix 8](#) provides samples SAS model statements for constructing the confidence interval for the proportion.

The comparisons of filgotinib 100 mg groups versus placebo group in the proportion of subjects achieving ACR20 at Week 12 will also be conducted with the similar logistic regression model with NRI as aforementioned.

The number and percentage of ACR20 non-responders observed and non-responders due to missing at Week 12 will also be summarized respectively by treatment.

For subjects with observed ACR20 outcomes (ie, responders and observed non-responders) at Week 12, actual values and change from Baseline at Week 12 in individual components, including TJC68, SJC66, SGA, PGA, Subject's pain assessment, hsCRP, will be summarized using descriptive statistics (sample size, mean, SD, median, Q1, Q3, minimum, and maximum) by treatment.

The proportions of subjects achieving ACR20 (using NRI) will be plotted over time from Baseline through Week 24 by treatment and by visit.

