1.2. Study Design

This is a randomized, double-blind, placebo- and active-controlled, Phase 3 study in adult male and female subjects with active RA who have an inadequate response to MTX (MTX-IR). The study is designed to evaluate the efficacy, safety, and tolerability of filgotinib as well as its effect on work productivity, fatigue, and quality of life.

Approximately 1650 subjects will be randomized in a 3:3:2:3 ratio to filgotinib 200 mg, filgotinib 100 mg, active comparator (adalimumab), or placebo to match (PTM) administered for up to 52 weeks, all in the context of a weekly stable dose of MTX:

- Filgotinib 200 mg group: filgotinib (200 mg q.d.) + PTM filgotinib 100 mg (PTM q.d.) + PTM adalimumab (PTM s.c. injection q2w) (N=450)
- Filgotinib 100 mg group: filgotinib (100 mg q.d.) + PTM filgotinib 200 mg (PTM q.d.) + PTM adalimumab (PTM s.c. injection q2w) (N=450)
- Active comparator group: PTM filgotinib 200 mg (PTM q.d.) + PTM filgotinib 100 mg (PTM q.d.) + adalimumab (40 mg s.c. injection q2w) (N=300)
- Placebo control group: PTM filgotinib 200 mg (PTM q.d.) + PTM filgotinib 100 mg (PTM q.d.) + PTM adalimumab (PTM s.c. injection q2w) (N=450)

Randomization will be stratified by geographic region, prior exposure to biologic disease modifying antirheumatic drugs (bDMARDs), and presence of rheumatoid factor (RF) or anti-CCP (cyclic citrullinated peptide) antibody (Ab) at screening.

At Week 14, subjects who have not achieved at least 20% improvement from Baseline in both swollen joint count (SJC) and tender joint count (TJC) will discontinue investigational study drug dosing but will continue with study visits and assessments per protocol. All subjects meeting this criterion who discontinue from investigational therapy are to receive standard of care treatment for their RA as determined by the investigator.

[figure not shown]
At Week 24, all subjects assigned to placebo + MTX will be reassigned 1:1 to either filgotinib 100 mg q.d. or 200 mg q.d. in addition to MTX in a blinded fashion and will continue in the study per protocol up to Week 52.

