1.3. Sample Size and Power

Sample size is determined based on the superiority test of filgotinib 200 mg compared to placebo based on the change from Baseline in mTSS at Week 24. When assuming a difference of 0.4 between filgotinib and placebo on change from Baseline in mTSS at Week 24 and a common standard deviation of 1.85, 450 subjects in each of the filgotinib 200 mg group and placebo control group are required to obtain 90% power at a 2-sided 0.05-level.

A sample size of 450 subjects in each of the filgotinib groups and placebo control group will provide over 95% power to detect an increase in ACR20 response rate of 45% to 65% between the placebo control group and the filgotinib group respectively, using a 2-sided 0.05-level test.

Based on {Liu 2014}, 450 subjects in each of the filgotinib 200 mg group and placebo group, and 300 subjects in the adalimumab group, will provide over 90% power at 2-sided 0.05 significance level to demonstrate that filgotinib 200 mg preserves more than 50% of the effect of adalimumab with respect to the response rate of DAS28(CRP) ≤ 3.2 at Week 12, assuming both filgotinib 200 mg and adalimumab groups have similar response rates of DAS28(CRP) ≤ 3.2 . Given this study has a placebo group, assay sensitivity can be established through a direct comparison of adalimumab to placebo.

In summary, the total planned sample size will be 1650 (450 for the filgotinib 200 mg, filgotinib 100 mg, placebo groups, and 300 for the active comparator group).

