3.3. Strata and Covariates

Subjects will be randomly assigned to treatment groups via the interactive web response system (IWRS) in a 3:3:2:3 ratio to filgotinib 200 mg, filgotinib 100 mg, adalimumab or PTM using a stratified randomization schedule. Stratification will be based on the following variables:

- Geographic region (**Group A** includes the following countries: Australia, Belgium, Canada, France, Germany, Ireland, Israel, Italy, Netherlands, New Zealand, Republic of Korea, South Africa, Singapore, Spain, Sweden, Switzerland, United Kingdom, and USA; **Group B** includes the following countries: Bulgaria, Croatia, Czech Republic, Estonia, Georgia, India, Moldova, Romania, Russia, Slovakia, Ukraine, Serbia, Hungary, Latvia and Poland; **Group C** includes the following countries: Argentina, Brazil, Chile, Colombia, Peru, Puerto Rico and Mexico; **Group D** includes the following countries: China, Hong Kong, Malaysia, Philippines, Taiwan, Thailand and Vietnam; **Group E** includes Japan;
- Prior exposure to bDMARDs (Yes or No)
- Presence of RF or anti-CCP Ab (Yes or No) (Presence of RF = No if RF < 15 IU/mL; Presence of anti-CCP Ab = No if anti-CCP Quant < 17 U/mL)

If there are discrepancies in stratification factor values between the IWRS and the clinical database, the values recorded in the clinical database will be used for analyses.

For efficacy endpoints, stratification factors and the baseline value of the efficacy variable(s) will be included as covariates in the efficacy analysis model, as specified in Section 6.

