 - If a subject takes standard of care medications due to inadequate response or discontinues from study treatment, treat data as missing from the point of inadequate response or study drug discontinuation (ie, on-treatment data defined above).
 - If a subject discontinues from the study, treat data as missing from the point of loss to follow-up onward.
- 4) Population-level summary: proportion difference for binary efficacy endpoints or mean difference in change from baseline for continuous efficacy endpoints between each filgotinib group and placebo group or adalimumab group if applicable.

The **Treatment-Policy Estimand** is defined as following. This is the secondary estimand for efficacy endpoints.

- 1) Population: Subjects in the FAS.
- 2) Variable: Primary and key secondary endpoints as well as some other secondary endpoints (see details in Section 6.2, 6.3 and 6.4)
- 3) Intercurrent events: The occurrence of an intercurrent event is irrelevant. All observed values will be used regardless of occurrence of an intercurrent event.
 - All observed values will be used regardless of occurrence of an intercurrent event (ie, All available data defined above).
 - If a subject discontinues from the study, treat data as missing from the point of loss to follow-up onward.
- 4) Population-level summary: Proportion difference for binary efficacy endpoint or mean difference in change from baseline for continuous efficacy endpoints between each filgotinib group and placebo group or adalimumab group if applicable.

The other secondary endpoints specified in both estimands include ACR50, ACR70, and the individual components of the ACR response.

To handle the missing data caused by the intercurrent events, the following analyses will be performed for both estimands:

- For binary endpoints, missing data will be treated as non-responder for the primary analysis. Sensitivity analyses including observed data only, last observation carry forward (LOCF), multiple imputation, and tipping point methods will be applied.
- For continuous endpoints, missing data will be handled using a mixed-effects model for the primary analysis. Sensitivity analyses, including using multiple imputation and tipping point methods, will be applied.

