6.3.2. Analysis Methods for Key Secondary Efficacy Endpoints

Hypothesis testing on the key secondary efficacy endpoints will commence after the testing on the primary efficacy endpoint reaches statistical significance, and will be performed according to the hierarchical testing principle at the 2-sided 0.05 level as described in Section 3.5. If a null hypothesis is not rejected, formal sequential testing will be stopped and only nominal significance will be reported for the remaining hypotheses.

For non-inferiority test of the proportion of subjects who achieve $\text{DAS28}(\text{CRP}) \leq 3.2$ at Week 12, the approach proposed by {Liu 2014} will be used to demonstrate that each filgotinib dose preserves more than 50% of the effect of adalimumab on the response rate of DAS28 (CRP) ≤ 3.2 at Week 12 using NRI. Let π_T , π_C and π_P denote the true response rates of DAS28 (CRP) ≤ 3.2 for filgotinib, adalimumab, and placebo respectively, at Week 12, with corresponding variances σ_T^2 , σ_C^2 and σ_P^2 . The non-inferiority null hypothesis is

$$H_{0,NI} : \frac{\pi_T - \pi_P}{\pi_C - \pi_P} \leq 0.5$$

According to {Liu 2014}, non-inferiority (filgotinib preserves more than 50% of the effect of adalimumab) at 2-sided 0.05 level will be claimed if $Z_{NI} > z_*$, where

$$Z_{NI} = \frac{\hat{\pi}_T - 0.5\hat{\pi}_C - (1-0.5)\hat{\pi}_P}{\sqrt{\hat{\sigma}_T^2 + 0.5^2\hat{\sigma}_C^2 + (1-0.5)^2\hat{\sigma}_P^2}}$$
 and z_* is the 97.5 quantile of the standard normal distribution.

Note that the “hat” (^) denotes the estimated values of each parameter at Week 12.

The non-inferiority test of the proportion of subjects who achieve $\text{DAS28}(\text{CRP}) < 2.6$ at Week 12 will be performed.

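### Binary superiority tests adjust for the randomisation strata, but the reported rate differences, their CIs and the non-inferiority statistic do not, so the CIs are slightly wide and the non-inferiority test slightly weak

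*SAP*

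**What the plan says.** Randomisation is stratified by region (five groups), prior bDMARD exposure and RF/anti-CCP status (SAP 3.3). The same section says that "stratification factors and the baseline value of the efficacy variable(s) will be included as covariates in the efficacy analysis model", and then refers to Section 6 for the specification.

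For binary endpoints the composite estimand's population summary is a "proportion difference for binary efficacy endpoints or mean difference in change from baseline for continuous efficacy endpoints" (SAP 6.1). The primary hypothesis is equality of two response rates, assessed by a "superiority test at the 2-sided 0.05-level" (6.2.2). The p-value comes from a logistic model with treatment and the stratification factors (6.2.3). The accompanying effect size is a "non-stratified ACR20 response rate difference along with its 95% CI calculated based on the normal approximation", and the sentence goes on to specify a pooled variance. SAP 6.2.4.1, 6.3.2 and 6.4.2 repeat this pairing. The Appendix 8 code is a treatment-by-response table with no stratum variable. Its formula is unpooled and continuity-corrected.

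The non-inferiority test must show that more than half of adalimumab's effect is preserved "on the response rate of DAS28 (CRP) ≤ 3.2 at Week 12 using NRI" (6.3.2). Its statistic contains one rate and one variance per arm and nothing for strata, as in Protocol 8.5.2. SAP 6.5 attributes the change from Cochran-Mantel-Haenszel to logistic regression to small cells. It gives no reason for leaving strata out of the difference or the non-inferiority statistic.

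**The concern.** The estimand is a difference in proportions, yet the model that supplies the p-value supplies no estimate of it. The model's coefficient is a conditional log odds ratio, while the reported effect is a marginal, unadjusted difference. After stratified randomisation, a variance formula that ignores prognostic strata overstates the sampling variance of that difference. The CI is then wider than the design warrants, and it can include zero when the adjusted test rejects.

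For non-inferiority, an overstated variance makes the statistic too small. Tests 8, 9, 16 and 17 in SAP 3.5 belong to a fixed sequence that stops at the first failure. Failing test 8 ends formal testing of tests 9 to 19, including SF-36 PCS, FACIT-Fatigue and superiority to adalimumab.

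**Working it through.** **Inputs from the documents.** Subjects are "randomized in a 3:3:2:3 ratio to filgotinib 200 mg", 100 mg, adalimumab and placebo, giving 450/450/300/450. Alpha is 0.05 two-sided. SAP 1.3 assumes ACR20 rates of 45% and 65%. The non-inferiority fraction is 0.5, and SAP 1.3 assumes similar filgotinib 200 mg and adalimumab rates without giving them.

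**Assumption.** R², the share of outcome variance explained by strata, is not in the documents. R² = Var(stratum rates)/[p(1−p)]. At p = 55%, R² of 1% and 8% correspond to stratum-rate SDs of √(0.01 × 0.2475) = 5 points and √(0.08 × 0.2475) = 14 points.

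**The plan's own figures reproduce.** For mTSS, with a difference of 0.4 and a "common standard deviation of 1.85, 450 subjects in each of the filgotinib 200 mg group and placebo control group", Φ(0.4/[1.85√(2/450)] − 1.96) = 90.0%. For ACR20 at 65% vs 45%, power is 99.998%, consistent with the stated figure of over 95%. Neither depends on this point. The stated non-inferiority power of over 90% cannot be checked exactly without rates. With equal active rates, 90% needs an effect over placebo of 17.7, 18.5, 19.0 or 19.3 points at placebo rates of 15%, 20%, 25% or 30%.

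**ACR20 CI half-widths at 65% vs 45%, 450 per arm.**
- Plain Wald: variance = 0.65×0.35/450 + 0.45×0.55/450 = 0.0010556; SE = 0.0325; 1.96 × SE = 6.37 points.
- Pooled variance, as in the text of 6.2.3: 1.96√(0.55×0.45×2/450) = 6.50 points.
- Appendix 8 formula: 6.37 + ½(1/450 + 1/450) = 6.37 + 0.22 = 6.59 points.
- With strata reflected, 6.37 × √(1−R²): 6.34 at 1%, 6.24 at 4%, 6.11 at 8%.

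**Bias, noise and coverage.** Stratified randomisation over 20 cells (5×2×2) was simulated with assumed stratum sizes and effects. Bias in the crude difference was about 0.1 point or less. At 8% explained, its true sampling SD was 0.0308 against 0.0307 for the Mantel-Haenszel difference, while the reported SE was 0.0325. Wald coverage was about 96%, in line with the analytic 1 − 2Φ(−1.96/√0.92) = 95.9%. With no true difference, the plain Wald CI excluded zero in 4.8%, 4.1% and 3.8% of trials at about 1%, 8% and 15% explained, so it is conservative.

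**Test against CI.** At a true 10-point difference, the adjusted p-value and the plain Wald CI disagreed in 0.2%, 1.6% and 4.3% of trials at about 1%, 8% and 15% explained (1.7%, 3.4% and 5.8% with the Appendix 8 correction). At 20 points they never disagreed.

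**Non-inferiority power.** With equal active rates and effect d over placebo, the contrast is 0.5d and V = p_T(1−p_T)/450 + 0.25·p_C(1−p_C)/300 + 0.25·p_P(1−p_P)/450. The crude statistic divides by √V although its true variance is (1−R²)V. Its power is therefore Φ[(0.5d/√V − 1.96)/√(1−R²)], and the adjusted power is Φ[0.5d/√((1−R²)V) − 1.96].

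| Placebo rate, effect | R² 4%: crude → adjusted | R² 9%: crude → adjusted |
|---|---|---|
| 15%, 20 points | 95.4% → 95.8% | 95.8% → 96.6% |
| 20%, 20 points | 94.1% → 94.5% | 94.5% → 95.5% |
| 25%, 20 points | 93.0% → 93.6% | 93.6% → 94.7% |
| 30%, 20 points | 92.5% → 93.0% | 93.0% → 94.2% |
| 25%, 14 points | 68.4% → 69.8% | 68.8% → 72.1% |

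For the last row, V = 0.000529 + 0.000198 + 0.000104 = 0.000831, √V = 0.0288 and 0.07/√V = 2.43.

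**The case against.** The strongest reply is that nothing decisive rests on the crude CI. SAP 6.3.2 assigns inference to the logistic p-value, and the difference is additional and openly labelled as non-stratified. Under a main-effects logistic model, a conditional odds ratio of one and equal response rates are the same null. That stands, and it disposes of the reading that test and CI address unrelated hypotheses or could plausibly conflict on ACR20 at the planned effect. Disagreement is a possibility only for small differences. It is most relevant to superiority over adalimumab (tests 14, 15, 18 and 19), since the sizing assumes similar DAS28 ≤3.2 rates.

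A reader might also infer that the crude difference is biased or noisier, or that type I error is inflated. The calculations show neither. Nor does SAP 3.3 contradict the non-inferiority formula: it defers to Section 6 and speaks of an analysis model, which this statistic is not. That the non-inferiority estimates are crude is inferred from a formula without a stratum term, because the variance estimators are not defined. For DAS28 <2.6, 6.3.2 says only that the test will be done, and a formula covering it appears in 6.3.3.3. Within the non-inferiority test, estimate and test agree.

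The larger gains need strong assumptions. An SD of 15 points produced by prior bDMARD exposure alone, at about 20% prevalence, would need a gap of 15/√(0.2×0.8) = 37.5 points. The gain of about 3 points arises at a 14-point effect, where power is already well below the stated 90%.

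Small cells are a fair argument against weighting 20 separate cells. They do not weigh against standardising from the model the SAP already fits.

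**Conclusion.** The point holds as a minor improvement that needs no new data. The effect size for the estimand does not come from the model that tests it, and the CI and the non-inferiority statistic, as written, forgo a small gain that the stratified design already provides. The error is conservative. Under the assumed 1% to 8% explained variance, the plain Wald half-width would shorten by 0.03 to 0.26 points. Non-inferiority power would rise by about 0.4 to 1.2 points at a 20-point effect for 4% to 9% explained, and by up to about 3 points at 14 points. The true figures depend on stratum effects that the documents do not give. The documents do not support reading this as an error that threatens a planned conclusion.

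The conflict over the crude CI's variance is certain from the text and of similar size: 6.50 points under the wording of 6.2.3 against 6.59 under Appendix 8.

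**What to change.** - In SAP 6.2.3, 6.2.4.1, 6.3.2 and 6.4.2, make the main estimate and 95% CI the rate difference standardised from the specified logistic model: average the predicted probabilities over all subjects in the analysis set under each treatment, with a delta-method SE. Keep the crude difference as a descriptive line.
- For tests 8, 9, 16 and 17, put the standardised proportions and their covariance matrix into the non-inferiority contrast, and define the variance estimator explicitly. List this in 6.5 as a change from the formula in Protocol 8.5.2.
- For the crude CI that is kept, choose either the pooled variance of 6.2.3 or the unpooled, continuity-corrected formula of Appendix 8, and state the same one in both places.

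The cost is SAP wording and programming before the Week 24 unblinding, with no new data. The non-inferiority change must also be carried through the observed-case, LOCF, multiple-imputation and tipping-point repeats in 6.3.3.2 and the series of margins in 6.3.3.3, so it is more than a one-line edit.
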